3.6 Exploratory Endpoints

Sub-hertz Analysis of ViscoElasticity (SAVE) in muscle tissue in response to local immunological reactions due to influenza vaccination

SAVE is a non-invasive imaging technique used to measure viscoelastic characteristics of tissue. This technique enables imaging biphasic characteristics of tissue which are related to both extracellular matrix changes as well as disruption in the interstitial fluid mobility due to structural changes. A clinical study of this method in breast tumors has shown to provide effective separation of the benign from malignant breast lesions in patients [25].

In this study, SAVE will be used for quantification of muscle reaction in response to vaccination, which usually occurs within few hours of injection. Vaccine potency and efficiency are estimated by antigen-specific antibody titers and T-cell responses generated weeks after vaccination. Skeletal muscle contains few immune cells, but tissue resident and/or infiltrating immune cells encounter vaccine antigens for the first time at the site of administration. Thus, the magnitude of local innate immune responses starting at the vaccine delivery site (local inflammation) initially controls subsequent adaptive immune responses and may be captured by SAVE.

- Comparison of SAVE between left versus right deltoid muscles of the same individual.

Markers of Cell Senescence

- Changes in markers of senescence in blood and urine.

Efficacy

- Reduction of COVID-19 morbidity (detection of viral infection by PCR)

3.7 Primary Safety Endpoints

Safety assessments are undertaken with the measurement of safety laboratory tests and procedures, vital signs, and recording of adverse events.

3.8 Identification of Source Data

Source data will be obtained from the electronic medical record and documented in study specific case report forms (paper and/or electronic data capture). No information in source documents about the identity of the subjects will be disclosed.

4 Subject Selection Enrollment and Withdrawal

4.1 Inclusion Criteria

Study candidates must meet all the following criteria within 1 week prior to entolimod administration to be eligible for participation in this study:

1. Men and women of age 65 years and older at the time of enrollment
2. Eligible to receive Fluzone High-Dose
3. Female subjects must be past menopause and not pregnant
4. No history of anaphylactic reaction to gelatin, neomycin, or other vaccine component
5. Must not have had the flu vaccine within the past 90 days
6. Medically stable with no exacerbations or changes in medication regimen for chronic diseases in the past 3 months and no hospitalizations in the past 6 months
7. Must be able to read/write English in order to provide informed consent and comply with study procedures
8. Expected to be available for the duration of the study

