1.6.1 Definition of DLT

Reference should be made to the Guidance for Industry Toxicity Grading Scale for Healthy Adult and Adolescent Volunteers Enrolled in Preventive Vaccine Clinical Trials for grading the severity of AEs and laboratory abnormalities where applicable. Based on the known safety profile of entolimod, flu-like symptoms are expected. Decreases in blood pressure, increases in heart rate, hepatic transaminase elevations, hyperglycemia, and hypophosphatemia are expected. DLT will be defined based on the sound clinical judgement of the investigator. DLTs will be considered adverse events and their time and grade severity will be recorded.

These risks and benefits are outlined in the Informed Consent Form and listed in the Investigators Brochure.

2 Study Objectives

Primary Objective

- To evaluate the effect of increasing dose of entolimod on enhancement of the influenza vaccine immunogenicity in the geriatric population (≥ 65 years old).

- To characterize the safety profile of entolimod within the geriatric population (≥ 65 years old) vaccinated against influenza.

Secondary Objectives

- To evaluate the pharmacodynamic effects of entolimod on immunological status, markers of senescence, viscoelasticity of tissue at the injection site, frailty indices and quality of life (QoL).

Exploratory Objectives

- To determine levels of anti-COVID-19 serum-circulating antibodies in a population of confirmed COVID-19 cases
- To determine the rate of the following occurrence in patients that become COVID-19 positive: (i) disease progression requiring hospitalization; (ii) acute respiratory distress syndrome (ARDS); (iii) and 30-day mortality following study drug administration.

3 Study Design

This clinical trial is a randomized, double-blind, placebo-controlled, dose-escalated, single-administration study evaluating the immunogenicity, pharmacodynamics, and safety of entolimod within the geriatric population (≥ 65 years old) vaccinated against influenza. After providing a written informed consent, subjects will undergo screening medical history, physical examination, vital signs, laboratory, and electrocardiogram (ECG) assessments within 28 days prior to study drug administration and influenza vaccination (see figure 2 below).

[figure not shown]

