4.2 Exclusion Criteria

Study candidates who meet any of the following criteria within 28 days prior to entolimod administration will not be eligible for participation in this study:

1. Receipt of any other vaccines within the past 30 days prior to enrollment
2. Acute illness within the last 7 days without systemic signs and symptoms including fever > 99.5
3. History of hypersensitivity to the flu vaccine or its components (including gelatin, formaldehyde, octoxinol, thimerosal, and chicken protein).
4. History of Guillain Barré syndrome (GBS)
5. History of bleeding disorders
6. Medical contraindication to treatment with vaccine as indicated by a history of autoimmune disease, immune deficiency, or hypersensitivity to other vaccines.
7. Unstable major cardiovascular, renal, endocrine, immunological or hepatic disorder
8. Systolic blood pressure (SBP) < 110 mmHg or orthostatic hypotension [>20 mmHg fall in SBP or >10 mmHg fall in diastolic blood pressure (DBP) with standing] at the time of screening.
9. Evidence of an ongoing systemic bacterial, fungal, or viral infection (including upper respiratory tract infections) (within 14 days prior to entolimod administration). **Note:** *Subjects with localized fungal infections of skin or nails are eligible.*
10. Baseline vital signs with \geq Grade 2 abnormalities
11. Significant cardiovascular disease (e.g., myocardial infarction, arterial thromboembolism, cerebrovascular thromboembolism, venous thromboembolism) within 6 months prior to study drug administration; symptomatic dysrhythmias or unstable dysrhythmias requiring

medical therapy; angina requiring therapy; symptomatic peripheral vascular disease; New York Heart Association Class 3 or 4 congestive heart failure; or uncontrolled Grade ≥ 3 hypertension (diastolic blood pressure ≥ 100 mmHg or systolic blood pressure ≥ 160 mmHg) despite antihypertensive therapy.

- a. Significant screening ECG abnormalities, including unstable cardiac arrhythmia requiring medication, atrial fibrillation, 2nd-degree atrioventricular (AV) block type II, 3rd degree AV block, or Grade ≥ 2 bradycardia (within 14 days prior to entolimod administration).
- 12. Inadequate hepatic function (within 14 days prior to entolimod administration):
 - a. Serum alanine aminotransferase (ALT) $\geq 3 \times$ upper limit of normal (ULN) (Grade ≥ 1).
 - b. Serum aspartate aminotransferase (AST) $\geq 3 \times$ ULN (Grade ≥ 1)

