6.1 Visit 1, Screening Visit (-28 to -7 days)

A tabulated summary of all visits and assessments described in the following sections is provided in Table S-1, Schedule of Events. To the extent possible, subjects will be expected to adhere to the established visit schedule.

After discussing the study with the investigator/appropriate study staff and after agreeing to study participation by signing the consent, subjects will be assigned a subject number. For any subject, it is the responsibility of the investigator or study team member to obtain written informed consent (subject's signature) prior to performing any protocol-mandated assessment.

However, assessments performed as part of the routine care of the subject may be used to assess eligibility. The subject number will identify the subject throughout the study. In case of re-screening, the subject number assigned during the first screening procedure will be retained.

Patients meeting the entry criteria and consenting to participate in the protocol will undergo the following:

- Eligibility confirmation and informed consent discussion and documentation
- Review of medications
- Brief Physical examination
- Medical history
- Respiratory infection assessment
- Demographic Information
- Quality of Life (QoL) questionnaire
- Mini-Mental State Examination (MMSE) cognitive status assessment
- ECG – assessment of QTc interval
- Vital signs (orthostatic blood pressure, temperature, respiratory rate, height, weight, oxygen saturation and heart rate)
- Blood work – screening labs [serum chemistry, hematology, coagulation, CMV, serum virology, cytokines, study drug related antibodies, long interspersed nuclear elements-(LINE-1), peripheral blood mononuclear cells (PBMCs) and biomarkers of senescence]
- Urine collection for urinalysis
- Frailty Assessments (includes questionnaires, physical function testing and body composition)

6.2 Visit 2, Treatment Visit – Day 0

This visit will be recorded as "Day 0" and will require a visit to the research center where the following tests will be performed:

- Vital signs (orthostatic blood pressure, oxygen saturation, temperature, respiratory rate, weight, and heart rate) prior to vaccine and investigational product administration and 2, 4 and 6 hours post administration
- Review of medications
- Review of adverse events
- Respiratory infection assessment
- COVID-19 Screening questionnaire
- Flu vaccine administration
- Investigational product administration
- Nasal swab

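### For screening on days -28 to -15, which section 6.1 allows, no scheduled ECG or liver test falls inside the 14-day limits of section 4.2

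*Combined protocol and SAP*

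**What the plan says.** **Windows on eligibility.** Section 4.1 opens with "Study candidates must meet all the following criteria within 1 week prior to entolimod administration to be eligible". Section 4.2 opens with a longer frame: "Study candidates who meet any of the following criteria within 28 days prior to entolimod administration will not be eligible". Inside that list, item 12 reads "Inadequate hepatic function (within 14 days prior to entolimod administration", and item 11a, on screening ECG abnormalities, ends "bradycardia (within 14 days prior to entolimod administration".

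**Windows on screening.** The heading of section 6.1 is "Visit 1, Screening Visit (-28 to -7 days". Section 3 is looser, with "electrocardiogram (ECG) assessments within 28 days prior to study drug administration and influenza vaccination" and no day -7 limit. Table S-1 shows -28 days.

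**What is scheduled before dosing.** Section 6.1 lists "Eligibility confirmation and informed consent discussion and documentation" at Visit 1, together with the ECG and serum chemistry. For Visit 2, section 6.2 lists vital signs, medication review, adverse event review, a respiratory infection assessment, a COVID-19 questionnaire, and blood for pharmacodynamics, antibodies, LINE-1 and PBMCs. It lists no eligibility confirmation, ECG or serum chemistry. Table S-1 agrees: these three are marked at screening and not at the treatment visit. The next ECG and chemistry come at Visit 3, the day after dosing.

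**The concern.** A look-back limit on a test works only if the schedule produces a test inside it. Here the limit is 14 days, the visit that supplies the test may fall up to 28 days before dosing, and no repeat ECG or chemistry is scheduled before the injection.

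Three things are at stake.

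- **Subject safety.** Transaminase elevation is a listed potential risk (section 1.6). The liver and ECG exclusions should be checked against results as recent as the protocol itself asks for.
- **Who counts as excluded.** Section 7.2 removes from all analyses patients who meet exclusion criteria after screening and randomization. If it is unclear which result on which day decides items 11a and 12, membership of the analysis set is open to dispute, with 25 subjects planned per arm.
- **The safety baseline.** Laboratory abnormalities and adverse ECG findings are primary safety endpoints (section 3.4). A laboratory adverse event is defined by a shift from a normal pre-treatment value (section 8.1), and QTc is summarized as change from baseline (section 8). The plan does not name the pre-dose sample used for these safety changes.

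**Working it through.** The plan states no figure to reproduce. The check is a count of calendar days, with dosing on Day 0 as in section 6.2.

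**Inputs**

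| Item | Value | Source |
|---|---|---|
| Screening window, narrower wording | day -28 to day -7 | section 6.1 |
| Screening window, looser wording | day -28 to day -1 | section 3 |
| ECG limit | 14 days before dosing | section 4.2, item 11a |
| Liver-test limit | 14 days before dosing | section 4.2, item 12 |
| Scheduled pre-dose ECG and chemistry | Visit 1 only | sections 6.1, 6.2, Table S-1 |

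**Step 1: length of the window.** Section 6.1: 28 - 7 + 1 = 22 days. Section 3: 28 - 1 + 1 = 28 days.

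**Step 2: days that miss the 14-day limit.** These are days -28 to -15, so 28 - 15 + 1 = 14 days under either wording.

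**Step 3: days that meet it.** Section 6.1: days -14 to -7, so 22 - 14 = 8 days. Section 3: days -14 to -1, so 28 - 14 = 14 days.

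| Wording | Days allowed | Inside 14 days | Outside 14 days |
|---|---|---|---|
| Section 6.1 | 22 | 8 | 14 (14/22 = 63.6%) |
| Section 3 | 28 | 14 | 14 (14/28 = 50.0%) |

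**Step 4: is there a later scheduled test?** No. Visit 2 has neither test, and Visit 3 comes after dosing. For any subject screened in the 14 days of step 2, no scheduled ECG or liver test falls inside the limit.

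**Step 5: which frame governs?** Suppose ALT is at or above the item 12 threshold on day -20. That result is inside the 28-day frame that opens section 4.2 and outside the 14 days of item 12. The text does not say which decides. Bilirubin (item 13), from the same chemistry panel, carries no 14-day limit.

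**Step 6: the 1-week rule.** Visit 1 as dated in section 6.1 overlaps the last week before dosing only on day -7. Formal confirmation of eligibility is listed at Visit 1 and not on Day 0.

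**The case against.** The best defence is that the windows can be followed as written. Section 6 lets screening procedures be spread over several days of the screening period and permits extra assessments. Section 6.1 accepts routine-care results for eligibility and provides for re-screening. A 28-day outer window with tighter limits for particular tests is common, and an ECG and chemistry on days -14 to -7 would satisfy both sections. This stands as far as it goes: compliance is possible. But no passage requires that placement, and section 6 says data from additional assessments will not necessarily be collected.

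Three stronger readings are tempting, and the documents do not support them.

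- **That only a screening on day -7 can meet the 1-week rule, so that 21 of 22 screening days fail it.** Section 4.1 asks that the criteria be met in that week, not that the visit take place in it. The eight items are status or history, such as age, menopause, past reactions, recent vaccination and medical stability. None needs a timed ECG or laboratory test. Day 0 lies inside the week, and its medication and adverse event reviews can bring part of any change to light. What remains is that no Day 0 eligibility confirmation is listed.
- **That most subjects would be protocol deviations.** The counts are of allowed days. The documents give no distribution of screening dates, and under section 3 the share of days outside 14 days is exactly half.
- **That an old baseline damages the safety comparison.** The documents give no figure for drift in chemistry or ECG over four weeks, and any drift since screening would also occur under placebo. Vital signs do have a same-day pre-dose value. The supportable point is only that the safety baseline is not named.

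**Conclusion.** The mismatch is real for two tests. Sections 6.1 and 6.2 and Table S-1, followed exactly, can lead to dosing a subject with no ECG or liver test inside the 14 days of section 4.2. It arises for screening on days -28 to -15: 14 of 22 allowed days under section 6.1, or 14 of 28 under section 3. The number of subjects affected cannot be derived from the documents.

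The missing Day 0 eligibility confirmation under section 4.1 is a lesser point of the same kind.

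The conclusion assumes that dosing is Day 0, that day -14 counts as within 14 days, and that the assessments listed in sections 6.1 and 6.2 and Table S-1 are the complete required set. It does not touch the sample size or the primary immunogenicity analysis. The plan should be corrected because, as written, the schedule does not ensure a safety check that the protocol itself sets.

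**What to change.** 1. Reconcile sections 3, 4.1, 4.2, 6.1 and 6.2 and Table S-1 so that the ECG, the liver tests and the eligibility confirmation are each scheduled at a time that meets the window stated for them. The clinical team sets those windows.
2. State in section 4.2 how the 28-day frame and the 14-day limits of single items work together, so that it is clear which result decides exclusion.
3. Name in section 7.2 or section 8 the pre-dose sample and ECG used as baseline for laboratory and QTc changes.

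The cost is wording and an edit to the schedule table. Depending on the team's choice, there may also be a change in when tests are done or a repeat ECG and chemistry for subjects screened early. Adding chemistry to the Visit 2 pre-dose draw would serve eligibility only if results were available before the injection, and it would not supply an ECG.

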4.2 Exclusion Criteria

Study candidates who meet any of the following criteria within 28 days prior to entolimod administration will not be eligible for participation in this study:

1. Receipt of any other vaccines within the past 30 days prior to enrollment
2. Acute illness within the last 7 days without systemic signs and symptoms including fever > 99.5
3. History of hypersensitivity to the flu vaccine or its components (including gelatin, formaldehyde, octoxinol, thimerosal, and chicken protein).
4. History of Guillain Barré syndrome (GBS)
5. History of bleeding disorders
6. Medical contraindication to treatment with vaccine as indicated by a history of autoimmune disease, immune deficiency, or hypersensitivity to other vaccines.
7. Unstable major cardiovascular, renal, endocrine, immunological or hepatic disorder
8. Systolic blood pressure (SBP) < 110 mmHg or orthostatic hypotension [>20 mmHg fall in SBP or >10 mmHg fall in diastolic blood pressure (DBP) with standing] at the time of screening.
9. Evidence of an ongoing systemic bacterial, fungal, or viral infection (including upper respiratory tract infections) (within 14 days prior to entolimod administration). **Note:** *Subjects with localized fungal infections of skin or nails are eligible.*
10. Baseline vital signs with \geq Grade 2 abnormalities
11. Significant cardiovascular disease (e.g., myocardial infarction, arterial thromboembolism, cerebrovascular thromboembolism, venous thromboembolism) within 6 months prior to study drug administration; symptomatic dysrhythmias or unstable dysrhythmias requiring

medical therapy; angina requiring therapy; symptomatic peripheral vascular disease; New York Heart Association Class 3 or 4 congestive heart failure; or uncontrolled Grade ≥ 3 hypertension (diastolic blood pressure ≥ 100 mmHg or systolic blood pressure ≥ 160 mmHg) despite antihypertensive therapy.

- a. Significant screening ECG abnormalities, including unstable cardiac arrhythmia requiring medication, atrial fibrillation, 2nd-degree atrioventricular (AV) block type II, 3rd degree AV block, or Grade ≥ 2 bradycardia (within 14 days prior to entolimod administration).
- 12. Inadequate hepatic function (within 14 days prior to entolimod administration):
 - a. Serum alanine aminotransferase (ALT) $\geq 3 \times$ upper limit of normal (ULN) (Grade ≥ 1).
 - b. Serum aspartate aminotransferase (AST) $\geq 3 \times$ ULN (Grade ≥ 1)
 - c. Serum alkaline phosphatase (ALP) $\geq 5 \times$ ULN (Grade ≥ 2)
- 13. Serum bilirubin $\geq 1.5 \times$ ULN (Grade ≥ 1)
- 14. Positive antiviral serology:
 - a. Positive hepatitis C virus (HCV) antibody or positive HCV ribonucleic acid (RNA) by quantitative PCR.
 - b. Positive hepatitis B surface antigen (HBsAg) and negative hepatitis B core (HBc) antibody or undetectable hepatitis B (HBV) deoxyribonucleic acid (DNA) by quantitative polymerase chain reaction (PCR) testing.
- 15. Positive human immunodeficiency virus (HIV) antibody.
- 16. Use of medication that might interact with the flu vaccine including (but not limited to) specifically: aminopyrine, phenytoin sodium, theophylline, and warfarin sodium.
- 17. Any ongoing treatment with immunosuppressive or immune-stimulant therapy
- 18. Ongoing use of systemic corticosteroids.
- 19. Blood or blood products given within the three months prior to vaccination and two months after vaccination
- 20. Current and/or expected receipt of chemotherapy, radiation therapy or any other cytotoxic or immunosuppressive therapy [i.e. more than 10 mg of prednisone given daily or on alternative days for 2 weeks or more in the past 3 months]
- 21. Receipt of another investigational pharmaceutical product within 60 days of treatment
- 22. Diagnosis of Parkinson's Disease, previous stroke, or significant cognitive impairment (defined as MMSE < 20)
- 23. Other concerns that in the opinion of the PI would preclude a subject from participating in study procedures or from completing the study.

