Limitations of current and developing vaccines can be overcome by increasing the initial or boosted antibody titers thereby increasing the antibody titers above the threshold required for efficacy. A recently completed study of entolimod alongside the tetanus-diphtheria vaccine (Td) with alum (anti-TT and anti-diphtheria) (IND 017372), demonstrated that a single intermuscular (IM) injection of entolimod was able to significantly increase levels of anti-tetanus and anti-diphtheria antibodies while producing no significant adverse effects in healthy adults (ages 18-64). Two subjects also reported subjective feelings of increased immunity (e.g decreased seasonal allergy symptoms and decreased incidence of upper respiratory infection (URI) and an improvement in their general well-being. Data from this study has prompted further investigation into the effects of entolimod on antibody generation in the geriatric population. Pre-clinical data have shown that in male swiss mice, a single week-long treatment with entolimod is capable of having positive long-term effects on their physiological frailty index [7].

Based on the collective nonclinical and clinical data with entolimod, it is hypothesized that its administration in combination with the influenza vaccine will be safe within the geriatric population and result in increased circulating influenza-specific antibodies.

Coronavirus Disease 2019 (COVID-19) Background

COVID-19 infection-related mortality has a strong dependence on age. The risk of death in the elderly is so high that COVID19-induced illness can potentially be defined as aging-related disease. Hence, therapeutic development of COVID19 prophylaxis should focus primarily on the elderly population. High vulnerability to COVID19 reflects inefficient immune responses of older people to viral infections, a well-recognized phenomenon named immune senescence [8]. In fact, older people have impaired immunization capabilities requiring the use of increased doses of vaccines; furthermore, they commonly have activated latent viruses that stay suppressed in younger people, such as hepatitis B (HBV) or cytomegalovirus (CMV). Today, there are no approved drugs for reverting immune senescence and the high vulnerability of older people to viral infections, together with their reduced capability to be protected by vaccination, remain unmet medical needs.

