6.11 Laboratory Assessments

The following laboratory assessments will be collected at the time points specified in the schedule of events. The Investigator will be provided all laboratory results and will review and assess out-of-range findings for clinical significance. Any post-baseline abnormal laboratory value assessed as clinically significant will be recorded as an AE.

Blood Tests:

- Serum Chemistry studies will include sodium, potassium, chloride, bicarbonate, BUN, creatinine, glucose, calcium, phosphorus, magnesium, total protein, albumin, ALT, AST, ALP, CK, LDH, GGT, total bilirubin, uric acid and CRP.
- Hematology parameters will include hematocrit, hemoglobin, erythrocyte count, absolute counts of leukocytes, neutrophils, lymphocytes, monocytes, eosinophils, basophils, platelet count.
- Coagulation studies will include PT and aPTT.
- Virology evaluation includes serum CMV, HIV antibody, HBsAg antibody, HBc antibody, HCV antibody, Subjects will a positive antibody evaluation for HBc or HCV should undergo evaluation for HBV DNA and for HCV RNA to determine if the antibody test may be falsely positive.
- PBMC Culture Supernatant Assessment will include 10 cytokine/chemokine mediators of adaptive immune function (IFN- γ , IL-1 β , IL-2, IL-4, IL-6, IL-8, IL-10, IL-12p70, IL-13 and TNF- α) test performed using Meso Scale Discovery, V-PLEX Proinflammatory panel human immunoassay kits.
- Serum for study related antibodies includes influenza antibody titers against A/H1N1, A/H3N2, and B viruses, LINE-1, and entolimod specific neutralizing antibodies.
- Plasma for cytokines will include G-CSF and IL-6 tests will be performed using the MSD assay platform as well as senescence biomarkers. These samples will be de-identified and shipped to the sponsor, GPI, in a coded format. Samples will be used for research purposes only as described in this protocol. The data will be reported to the Mayo Clinic team for the analysis. When the study is completed, the sponsor will destroy any remaining samples.
- COVID-19 testing will include COVID-19, PCR [SARS Coronavirus 2, Molecular Detection, PCR (NP)] and SARS-CoV-2 IgG Ab [SARS Coronavirus 2 IgG Ab, Serum]

Urine Tests:

- Urinalysis will include specific gravity, pH, protein, glucose, ketones, bilirubin, urobilinogen, blood, nitrate, leukocyte esterase as assessed by dipstick and microscopic urinalysis evaluating white blood cells, epithelial cell, bacteria, casts, and crystals.

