[b] Physical examination will be limited to cardiac, pulmonary, abdominal, integumentary, and gross neurological evaluation, and to other systems based on specific subject complaints.
[c] Height will only be collected at screening; weight will be collected at all in-person visits
[d] To be collected pre-treatment and 2, 4 and 6 hours post treatment. Wt will only be performed prior to study drug administration.
[e] Serum chemistry studies will include sodium, potassium, chloride, bicarbonate, BUN, creatinine, glucose, calcium, phosphorus, magnesium, total protein, albumin, ALT, AST, ALP, CK, LDH, GGT, total bilirubin, uric acid, and CRP.
[f] Hematology parameters will include hematocrit, hemoglobin, erythrocyte count; absolute counts of leukocytes, neutrophils, lymphocytes, monocytes, eosinophils, basophils; platelet count.
[g] Coagulation studies will include PT and aPTT.
[h] Virology evaluation includes serum CMV, HIV antibody, HBsAg antibody, HBC antibody, HCV antibody. Subjects with a positive antibody evaluation for HBC or HCV should undergo evaluation for HBV DNA and for HCV RNA to determine if the antibody test may be falsely positive. Only CMV testing will be carried out on months 1 and 2.
[i] Urinalysis will include specific gravity, pH, protein, glucose, ketones, bilirubin, urobilinogen, blood, nitrite, leukocyte esterase as assessed by dipstick and microscopic urinalysis evaluating white blood cells, red blood cells, epithelial cells, bacteria, casts, and crystals.
[j] Test will be performed by GPI. Samples may also be used for additional testing related to the study objectives.
[k] G-CSF and IL-6 tests will be performed using the MSD assay platform. Samples are to be collected pre-treatment and 2, 4 and 6 hours post treatment.
[l] Influenza antibody titers A/H1N1, A/H3N2, and B assessed by HAI Assay
[m] Meso Scale Discovery, V-PLEX Proinflammatory panel for 10 cytokine/chemokine mediators of adaptive immune function (IFN- γ , IL-1 β , IL-2, IL-4, IL-6, IL-8, IL-10, IL-12p70, IL-13 and TNF- α) and Interferon gamma ELISPOT assay
[n] Sub-hertz Analysis of ViscoElasticity (SAVE) will be performed 6 hours after study drug administration (or placebo) on left and right deltoid muscles in cohorts receiving entolimod (3 μ g and 10 μ g) and representing a total of 50 subjects.
[o] Blood and urine will be collected for analyses of senescence
[p] Subjects will be contacted bi-weekly via the telephone for remote follow-up visits

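### Hepatitis B exclusion 14b runs the wrong way: under either reading it never excludes an HBc-positive subject with detectable HBV DNA

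*Combined protocol and SAP*

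**What the plan says.** Section 4.2 is an exclusion list in which meeting any one item makes a candidate ineligible. Item 14 concerns positive antiviral serology and has two parts:

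- **14a (hepatitis C)** excludes on "Positive hepatitis C virus (HCV) antibody or positive HCV ribonucleic acid (RNA) by quantitative PCR".
- **14b (hepatitis B)** excludes on "Positive hepatitis B surface antigen (HBsAg) and negative hepatitis B core (HBc) antibody or undetectable hepatitis B (HBV) deoxyribonucleic acid (DNA") by quantitative PCR.

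Section 6.11 says that subjects with a positive HBc or HCV antibody "should undergo evaluation for HBV DNA and for HCV RNA to determine if the antibody test may be falsely positive". Footnote [h] of Table S-1 repeats the order: "Subjects with a positive antibody evaluation for HBC or HCV should undergo evaluation for HBV DNA and for HCV RNA".

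No other eligibility criterion names hepatitis B. Two general items could bear on it: item 9, "Evidence of an ongoing systemic bacterial, fungal, or viral infection (including upper respiratory tract infections") within 14 days before entolimod, and item 23, "Other concerns that in the opinion of the PI would preclude a subject from participating in study procedures" or completing the study. Items 7, 12 and 13 deal with unstable hepatic disease and raised liver tests.

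**The concern.** Under a heading about positive serology, the HBc term asks for a negative result and the DNA term for an undetectable one. The sister item 14a works in the expected direction, with a positive nucleic acid result excluding. In 14b the DNA result that signals active infection never triggers exclusion, and the reassuring result can.

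The missing brackets add a second problem, because two coordinators could apply the sentence differently.

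What is at stake is safety screening. Section 1.1 says of older people that "they commonly have activated latent viruses that stay suppressed in younger people, such as hepatitis B (HBV) or cytomegalovirus (CMV"), so the item is relevant to this age group. The trial gives an immune stimulant for which section 1.6 lists transaminase elevation as a potential risk. Staff who follow the laboratory schedule can hold a detectable HBV DNA result and find that the one hepatitis B rule does not exclude on it.

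**Working it through.** **Inputs.** The wording of 14b comes from section 4.2. The rule for when HBV DNA is measured (only after a positive HBc antibody) comes from section 6.11 and Table S-1 footnote [h]. The plan states no figure here to reproduce, so the check is a truth table.

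**Notation.** S = HBsAg positive; C = HBc antibody positive; D = HBV DNA detectable; a minus sign marks the opposite result; nt = DNA not scheduled because HBc is negative (an untested DNA result is taken as not meeting a DNA condition).

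**Rules compared.**

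- Reading A (the more natural): S+ and (C− or D−)
- Reading B: (S+ and C−) or D−
- Proposed wording: S+ or (C+ and D+)

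**Observable patterns.** There are four with HBc positive and two with HBc negative.

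| HBsAg | HBc | HBV DNA | Reading A | Reading B | Proposed |
|---|---|---|---|---|---|
| + | + | detectable | passes | passes | excluded |
| + | + | undetectable | excluded | excluded | excluded |
| − | + | detectable | passes | passes | excluded |
| − | + | undetectable | passes | excluded | passes |
| + | − | nt | excluded | excluded | excluded |
| − | − | nt | passes | passes | passes |
| **Excluded, of 6** | | | **2** | **3** | **4** |

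**Results.**

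1. Rows 1 and 3 are the HBc-positive, DNA-detectable patterns. 14b excludes 0 of 2 under A, 0 of 2 under B; the proposed wording excludes 2 of 2. The reason is general: with C+ and D+, both 'C−' and 'D−' are false, so A reduces to S+ and false, and B to false or false.
2. Rows 1 and 2 differ only in DNA. Both readings exclude the undetectable result and pass the detectable one. Row 1 is the subject positive on every hepatitis B marker.
3. A and B disagree on one pattern, row 4.

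**If DNA were known for everyone** (8 patterns), Reading A would exclude 3 and Reading B 5. Reading B's 5 would include the subject negative on all three markers. The two HBc-positive, DNA-detectable patterns would still pass under both.

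**Would changing single words repair it?**

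- Change only 'undetectable' to 'detectable': A becomes S+ and (C− or D+), B becomes (S+ and C−) or D+. They exclude 2 and 3 of 6, and row 2 (S+, C+, D−) becomes eligible under both.
- Change 'negative' to 'positive' as well: A becomes S+ and (C+ or D+), B becomes (S+ and C+) or D+. Again 2 and 3 of 6, and row 5 (S+, C−) becomes eligible under both.

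Neither edit gives a sound rule, so the sentence has to be rewritten as a whole.

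**The case against.** The strongest answer is that item 9 already covers the case. Detectable HBV DNA is, on a plain reading, evidence of an ongoing viral infection, and item 9 is mandatory rather than a matter of opinion. The reflex DNA test, ordered to see whether an antibody result is false, also implies that a confirmed positive counts against the candidate. On this view the gap lies in one sub-item and not in eligibility as a whole. This largely stands as a limit on harm: item 9, with item 23 behind it, would probably keep a viraemic subject out. But item 9 names neither hepatitis B nor HBV DNA, so someone must decide that it applies, against a specific item that points the other way.

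It can also be said that only the DNA term is clearly inverted, because excluding HBsAg-positive, HBc-negative subjects is acceptable. That is fair for that one pattern. The HBc term still runs against the item's heading and helps let HBsAg-positive, HBc-positive subjects through.

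Further limits also stand:

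- Item 7 ("Unstable major cardiovascular, renal, endocrine, immunological or hepatic disorder") and items 12 and 13 give partial cover, but a viraemic subject passes 12 and 13 if ALT and AST are below 3 times, ALP below 5 times and bilirubin below 1.5 times the upper limit of normal.
- Dosing is single, and chemistry is repeated on Day 1 and at Months 1, 2, 6 and 12.
- Section 1.4.2.1 describes the transaminase rises as transient and without serious clinical implications, and section 1.6 draws that risk from doses 5 to 50 times those used here.
- The counts out of six are logical patterns, not frequencies.

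These points lower the weight of the error. They do not make the rule correct.

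**Conclusion.** The concern holds. Item 14b is wrong as written. Under either grouping it excludes 0 of the 2 HBc-positive, DNA-detectable patterns, and between two HBsAg-positive, HBc-positive candidates it removes the non-viraemic one.

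The logical result needs no assumption. The six-pattern count assumes that HBV DNA is measured only where the protocol orders it. The documents give no hepatitis B prevalence, so no number of affected subjects can be estimated; given the other exclusions, few if any of the 100 are likely to be affected. Allocation is randomised, so treatment contrasts are not biased, and no efficacy, alpha or power figure changes. It should be corrected because it is an operative safety rule that gives the wrong answer and is cheap to repair.

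**What to change.** Replace 14b with: *Positive HBsAg, or positive HBc antibody with detectable HBV DNA by quantitative PCR.*

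The present text looks like an eligibility condition carried into an exclusion list: HBsAg negative, and either HBc negative or DNA undetectable. That is an inference, but the logical negation of that condition is exactly the proposed wording. It keeps HBsAg-negative, HBc-positive subjects with undetectable DNA eligible. The clinical team should confirm that every HBsAg-positive subject is to be excluded.

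Two optional clarifications fit in the same edit: whether a negative HCV RNA result restores eligibility under 14a, and naming the surface marker as HBsAg, not as an antibody to it, in section 6.11 and footnote [h].

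The cost is one sentence in an IRB amendment, with no new test. Section 3 reports four subjects already accrued, so the screening serology of everyone enrolled to date should also be checked against the corrected rule.
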